11.6 Regulatory Documentation

Prior to implementing the protocol at each PNOC institution, the protocol, informed consent form, HIPAA authorization and any other information pertaining to participants must be first approved by the UCSF Institutional Review Board (IRB) and by the PNOC operations office. Prior to implementing this protocol at the participating sites, approval for the UCSF IRB approved protocol must be obtained from the participating site's IRB.

Appendix B lists the documents which must be provided to PNOC Operations Office before the participating site can be initiated and begin enrolling participants.

Upon receipt of the required documents, PNOC operations office will formally contact the site and grant permission to proceed with enrollment.

12 Protection of Human Subjects

12.1 Protection from Unnecessary Harm

Each clinical site is responsible for protecting all subjects involved in human experimentation. This is accomplished through the IRB mechanism and the process of informed consent. The IRB reviews all proposed studies involving human experimentation and ensures that the subject's rights and welfare are protected and that the potential benefits and/or the importance of the knowledge to be gained outweigh the risks to the individual. The IRB also reviews the informed consent document associated with each study in order to ensure that the consent document accurately and clearly communicates the nature of the research to be done and its associated risks and benefits.

Appendix A Performance Status Criteria

Karnof	sky	Lansky		
Score	Description	Score	Description	
100	Normal, no complaints, no evidence of disease	100	Fully active, normal.	
90	Able to carry on normal activity, minor signs or symptoms of disease.	90	Minor restrictions in physically strenuous activity.	
80	Normal activity with effort; some signs or symptoms of disease.	80	Active, but tires more quickly	
70	Cares for self, unable to carry on normal activity or do active work.	70	Both greater restriction of and less time spent in play activity.	
60	Required occasional assistance, but is able to care for most of his/her needs.	60	Up and around, but minimal active play; keeps busy with quieter activities.	
50	Requires considerable assistance and frequent medical care.	50	Gets dressed, but lies around much of the day; no active play, able to participate in all quiet play and activities.	
40	Disabled, requires special care and assistance.	40	Mostly in bed; participates in quiet activities.	
30	Severely disabled, hospitalization indicated. Death not imminent.	30	In bed; needs assistance even for quiet play.	
20	Very sick, hospitalization indicated. Death not imminent.	20	Often sleeping; play entirely limited to very passive activities.	
10	Moribund, fatal processes progressing rapidly.	10	No play; does not get out of bed.	

Appendix B PNOC Institutions Required Regulatory Documents

Before you can start enrollment at your site you must submit the following documents to PNOC:

Participating Site IRB approval(s) for the protocol, appendices, informed consent form and HIPAA authorization

Participating Site IRB approved consent form

Participating Site IRB membership list

Participating Site IRB's Federal Wide Assurance number and OHRP Registration number

Copy of the 1572 (Note: 1572 form is not required for FDA-exempt trials)

Curriculum vitae and medical license for each investigator and consenting professional

Documentation of Human Subject Research Certification training for investigators and key staff members at the Participating Site

Participating site laboratory certifications and normals

Signed copy of the completed delegation of authority log (found in PNOC Documents > Forms)

Signed copy of the protocol signature page

Signed copy of the final contract

Upon receipt of the required documents, PNOC will formally contact the site and grant permission to proceed with enrollment. All documents can be uploaded directly to SharePoint by navigating to your site's page and clicking "Add Documents"

Each PNOC site is responsible for ensuring all regulatory documents in SharePoint are up to date. Sites will upload new or revised documents as applicable to reflect any changes, including changes in staff and approved/expired documents.

Appendix C Required Data and Time Table for Submission

Form	Submission Timeline
Eligibility Checklist	Complete prior to registration
On Study Forms	Within 14 business days of registration
Baseline Assessment Forms	Within 14 business days of registration
Treatment Forms	Within 10 business days of the last day of the cycle
Adverse Event Report Forms	All AEs are due within 10 business days of the date of assessment.
Serious Adverse Event Reporting	Please refer to section on Expedited Reporting.
Response Assessment Forms	Within 10 business days of the completion of the cycle required for response evaluation
Off Treatment/Off Study Forms	Within 14 business days of completing treatment or being taken off study for any reason
Follow up/Survival Forms	Within 14 business days of the protocol defined follow up visit date

Appendix D PNOC Data and Safety Monitoring

PNOC Data Safety and Monitoring Plan for a Phase 1 Study

It is the responsibility of each PNOC member institution to follow the National Cancer Institute (NCI) approved Data Safety and Monitoring Plan (DSMP) for their site. For PNOC trials in which the UCSF PI holds the IND, the UCSF DSMC will be responsible for monitoring all participating sites, including UCSF. Remote institutions will be electronically monitored unless there are significant findings or issues identified that warrant an in-person visit. In addition to the guidelines laid out in this document, each PNOC member institution must comply with the policies and standards put forward by their own institutional DSMC/DSMB.

The UCSF DSMC/DSMB activities for this study will include:

- Monitoring every month/six months through the DLT period (depending on subject accrual)
- Review of suspected adverse reactions considered "serious" (SAEs)
- Minimum of a biennial regulatory audit

Monitoring and reporting guidelines

All institutional Phase 0 or Phase 1 therapeutic studies are designated with a high risk assessment. The data is monitored monthly by the UCSF DSMC/DSMB as subjects are enrolled and includes all visits monitored up through the Dose Limiting Toxicity (DLT) period.

The UCSF Helen Diller Family Comprehensive Cancer Center (HDFCCC) DSMC is responsible for monitoring data quality and patient safety for all HDFCCC institutional clinical studies. In the case of all PNOC protocols, the UCSF DSMC will work together with the non-UCSF PNOC member institution in order to ensure DSMP compliance. The UCSF DSMC/DSMB will be responsible for generating regular monitoring reports. These reports will be used by the UCSF DSMC to assess data quality, patient safety, and protocol compliance as well as to make decisions about dose escalations, where applicable.

PNOC and the UCSF DSMC reserve the right to conduct on-site monitoring at any non-UCSF member institution if DSMP requirements are not being met. If the need to perform a monitoring visit at a non-UCSF member institution arises, source documents will be provided by the member institution prior to the visit in order for the UCSF DSMC to monitor protocol compliance, patient safety, and to verify data entry.

The PNOC Operations Office provides administration, data management, and organizational support for the PNOC member institutions in the conduct of any PNOC clinical trial. The PNOC Operations Office will summarize and communicate adverse events, safety data, and other study matters to the PNOC member institutions on a quarterly basis.

The Study Chair is responsible for the overall conduct of any PNOC trial and for monitoring its safety and progress at all participating sites (as outlined in the PNOC Study Chair and Co-Chair Responsibilities SOP). The Study Chair will conduct continuous review of data and subject safety and

discuss each subject's treatment with the PNOC Operations Office. The discussions are documented in the PNOC Operations Office meeting minutes.

Multicenter communication

The PNOC Operations Office will coordinate, at minimum, quarterly conference calls with the PNOC member institutions to discuss risk assessment. The following items will be discussed, as appropriate:

- Enrollment information
- Cohort updates (e.g. DLTs and dose escalations)
- Adverse Events (e.g. new AEs, unresolved AEs, and new safety information)
- Protocol violations
- Other study conduct issues

Dose level considerations

Dose level assignments for any subject scheduled to begin treatment **must be confirmed** by the PNOC Operations Office via e-mail.

If an unexpected Dose Limiting Toxicity (DLT) arises in a subject treated at any participating PNOC member institution, all member institutions must be notified of the DLT by the PNOC Operations Office within **1 business day**. Member institutions will otherwise be provided with final DLT reports as they become available.

Adverse event review and monitoring

PNOC uses the web-based OnCore® Clinical Trials Management System for all patient registrations and the Advarra EDC for data entry. The OnCore® System will also track patient level protocol compliance and safety information. The Advarra EDC system is CFR part 11 compliant. For Phase I studies, all clinically significant Adverse Events (AEs) will be entered into the Advarra EDC, regardless of relationship. All Adverse Events entered into Advarra® will be reviewed on a weekly basis by the PNOC Operations Office. The PNOC Operations Office will discuss the toxicity, grade, and relationship to study intervention for all AEs in question.

All Adverse Events must be entered into Advarra® within **10 business days** of becoming aware of the event. Member institutions will submit this information to PNOC via the Adverse Event Form within Advarra®.

In addition, all adverse reactions considered "serious" (also called Serious Adverse Events, or SAEs), regardless of relationship, must be entered in OnCore® and Advarra, and reported to the PNOC Operations Office within **1 business day**. SAEs will be reviewed and monitored by the UCSF DSMC on an ongoing basis, and will be discussed at the UCSF DSMC meeting, which take place every six (6) weeks.

If a death occurs during the treatment phase of the study, or within 30 days after the last administration of the study drug(s), and is determined to be related either to the investigational drug or to any research related procedure, the Study Chair and the PNOC Operations Office must be notified by the member institution within **1 business day.** The Study Chair or the PNOC Operations Office must then notify the

UCSF DSMC Chair, or qualified alternate, within 1 business day of this notification. The contact may be by phone or e-mail.

Increase in adverse event rates

If an increase in the frequency of Grade 3, 4, or 5 Adverse Events (above the rate reported in the Investigator Brochure or package insert), the Study Chair or the PNOC Operations Office is responsible for notifying the UCSF DSMC at the time the increased rate is identified.

If at any time the Study Chair or the PNOC Operations Office halts enrollment or ends the study due to safety issues, the UCSF DSMC Chair and Manager must be notified within **1 business day** via e-mail. The UCSF DSMC must receive a formal letter within **10 business days**, and the UCSF IRB must be notified.

UCSF data and safety monitoring committee contacts:

Appendix E Specimen Collection Immuno-Monitoring

Sampling and Shipping information

- Blood for *in vitro* assays: up to 50-60 ml of blood (7 x 10 cc green top tubes: each tube should be filled as much as possible) for mononuclear cell preservation (before injection of vaccines). The volume will depend on the weight of the child based on the justification below. These samples will be sent to UCSF. Please refer to the PNOC member site SharePoint for details regarding shipping instruction and collection.
- Blood for circulating tumor DNA we will collect 6-7 ml at baseline and with each MRI assessment (- 7 days). Please refer to the PNOC members SharePoint site for details regarding shipping instruction and collection.

The minimum age enrolling in this trial is 3 years. The mean blood volume for a child is about 80 ml/kg. Up to 5% of total blood volume over a 24 hour period and up to 10% of the whole blood volume over an 8 week period might be removed for laboratory evaluations if the subject has a normal hematocrit ⁴¹. Based on our experience children with DIPG undergoing focal radiation have a normal hematocrit and since these children are not receiving any other therapies we anticipate that these children all have a normal hematocrit.

Based on the WHO criteria the weights based on the 50% percentile are as follows:

3 year old approximately 14 kg

4 year old approximately 16 kg

5 year old approximately 8 kg

The total blood volume for a 3 year old child is about 80x 14 kg = 1,120 ml. 5% of 56 ml; 10%112 ml.

The total blood volume for a 4 year old child is about 80x 16 kg = 1,280 ml. 5% of 64 ml, 10%128ml.

The total blood volume for a 5 year old child is about 80x 18 kg = 1,440ml. 5% of 72 ml; 10% 144 ml.

Based on these recommendations we will take 50 cc in green top tubes in children < 16 kg and 60cc in children >/= 16 kg for the immune-monitoring. We will assure that recommended dose of 5% of total volume in a 24 hour period will not be exceeded. ctDNA and other laboratory evaluations will be scheduled on different days as required by the guidelines.

Sample Shipment Instructions

Please refer to the PNOC member website SharePoint for details regarding shipping of collected specimens.

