3.2.1 Inclusion Criteria

Stratum A:

 Newly diagnosed children (3-21 years old) with DIPG who are positive for the H3.3K27M mutation (positive testing from a CLIA or equivalent laboratory required) that underwent standard radiation therapy.

Stratum B:

• Newly diagnosed children (3-21 years old) with diagnosis of midline glioma other than DIPG who are positive for the H3.3K27M mutation (positive testing from a CLIA or equivalent laboratory required), including spinal cord gliomas, that underwent standard radiation therapy.

Stratum C:

• Newly diagnosed children 3-21 years of age with diagnosis of DIPG or midline glioma other than DIPG (excluding primary spinal cord gliomas) who are positive for the H3.3K27M mutation (positive testing from a CLIA or equivalent laboratory required), that underwent standard radiation therapy.

The following eligibility criteria apply to strata A, B and C:

- The patient must test positive for HLA-A*02:01 (positive testing from a CLIA or equivalent laboratory required; only the HLA A*02:01 subtype is eligible; other subtypes are excluded)
- The patient must be either off systemic steroids or be on stable dose of dexamethasone or equivalent (max 0.1 mg/kg/day; maximum 4mg/day) at time of enrollment.
- Patients must not have received any prior chemotherapy, immunotherapy or bone marrow transplant for the treatment of their tumor. Prior use of temozolomide during radiation at maximum of the standard pediatric dosing (defined as 90 mg/m² /dose continuously during radiation therapy for 42 days) or dexamethasone is allowed.
- Patients must have undergone radiation therapy and surgery as part of their standard of care.

- Stratum A: Radiation therapy must have started within 4 weeks of diagnosis by imaging or surgery, whichever is later.
- Stratum B: For subjects undergoing surgery for more extensive resection, radiation therapy should be started within 4-6 weeks from surgery.
- Stratum C: Radiation therapy must have started within 4 weeks of diagnosis by imaging or surgery, whichever is later. For subjects undergoing surgery for more extensive resection, radiation therapy should be started within 4-6 weeks from surgery.
- Karnofsky ≥50 for patients ≥16 years of age, and Lansky ≥50 for patients < 16 years of age (See Appendix A). Patients who are unable to walk because of paralysis, but who are up in a wheelchair, will be considered ambulatory for the purpose of assessing the performance score.

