- The patient must have adequate organ function defined as:

Adequate Bone Marrow Function Defined as:

- Peripheral absolute neutrophil count (ANC) ≥ 1000/mm³ and
- Platelet count ≥ 100,000/mm³ (transfusion independent, defined as not receiving platelet transfusions for at least 7 days prior to enrollment).

Adequate Renal Function Defined as:

- Creatinine clearance or radioisotope GFR ≥ 70mL/min/1.73 m² or
- A serum creatinine based on age/gender as follows:

Age	Maximum Serum Creatinine	
	Male	Female
3 to < 6 years	0.8	0.8
6 to < 10 years	1	1
10 to < 13 years	1.2	1.2
13 to < 16 years	1.5	1.4
≥ 16 years	1.7	1.4

The threshold creatinine values in this table were derived from the Schwartz formula for estimating GFR utilizing child length and stature data published by the CDC.

Adequate Liver Function Defined as:

- Bilirubin (sum of conjugated + unconjugated) ≤ 1.5 x upper limit of normal (ULN) for age **and**
- SGPT (ALT) ≤ 110 U/L and
- Serum albumin \geq 2 g/dL.

Adequate Pancreatic Function Defined as:

• Serum lipase \leq ULN at baseline.

Adequate Pulmonary Function Defined as:

• No evidence of dyspnea at rest, no exercise intolerance due to pulmonary insufficiency, and a pulse oximetry of > 92% while breathing room air.

Adequate Neurologic Function Defined as:

- Patients with seizure disorder may be enrolled if seizure disorder is well controlled.
- The effects of the H3.3K27M vaccine and nivolumab on the developing human fetus are unknown. For this reason, females of child-bearing potential and males must agree to use adequate contraception. Adequate methods include: hormonal or barrier method of birth control; or abstinence prior to study entry and for the duration of study participation. Should a woman become pregnant or suspect she is pregnant while she or her partner is participating in this study, she should inform her treating physician immediately. Males treated or enrolled on this protocol must also agree to use adequate contraception prior to the study and for the duration of study participation.
- Ability to understand a written informed consent document, and the willingness to sign it. Assent will be obtained when appropriate based on the subjects age.

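### Appendix E's blood-draw limits require a normal hematocrit, but the plan assumes this for every child and no rule links the scheduled CBC to the research draw

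*Combined protocol and SAP*

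**What the plan says.** Appendix E sets the research blood volumes. Its limits, 5% of total blood volume in 24 hours and 10% over 8 weeks, describe what "might be removed for laboratory evaluations if the subject has a normal hematocrit". The condition is treated as satisfied on two grounds: the investigators' experience of children with DIPG after focal radiation, and the expectation that "since these children are not receiving any other therapies we anticipate that these children all have a normal hematocrit".

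Volume is then fixed by weight: "we will take 50 cc in green top tubes in children < 16 kg and 60cc in children >/= 16 kg for the immune-monitoring". For ctDNA, "we will collect 6-7 ml at baseline and with each MRI assessment". Appendix E also undertakes to stay within the 5% daily limit and to put ctDNA and other laboratory tests on different days.

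Other sections bear on the assumption:

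- Section 3.2.1 permits "Prior use of temozolomide during radiation at maximum of the standard pediatric dosing", for up to 42 days.
- Section 3.2.1 defines adequate marrow function by neutrophils and platelets only.
- Section 3.2.1 admits midline gliomas other than DIPG to Stratum C, including after more extensive resection.
- Section 6 gives Stratum C nivolumab every 3 weeks for up to 96 weeks.
- Sections 7.1.2.3 to 7.1.2.6 and Table 6.1 require a CBC at treatment visits and accept one from the previous 7 days.

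**The concern.** The normal-hematocrit condition is what makes the 5% and 10% limits applicable. The plan replaces it with an expectation, and the grounds for that expectation are narrower than the population. Nothing at eligibility excludes a child with a low red-cell count, and no later step changes the volume for one. The undertaking to stay within 5% does not help, because that limit presupposes the same condition.

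What is at stake is a participant-safety rule for research-only sampling in children as young as 3. The point has no bearing on sample size, power or type I error.

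**Working it through.** **Inputs.** From Appendix E: 80 ml/kg; weights of 14, 16 and 18 kg for ages 3, 4 and 5; draws of 50 cc below 16 kg and 60 cc from 16 kg; ctDNA 6-7 ml; limits of 5% and 10%. The weight list gives 8 kg for a 5-year-old, but the calculation beneath it uses 18 kg, so the 8 is a slip. From Table 6.2: immune draws at weeks 0, 12, 18 and 24, then every 12 weeks.

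**Step 1: reproduce the plan's figures.** Blood volume = 80 × weight; limits = 5% and 10% of it.

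| Weight | Blood volume | 5% | 10% |
|---|---|---|---|
| 14 kg | 1,120 ml | 56 ml | 112 ml |
| 16 kg | 1,280 ml | 64 ml | 128 ml |
| 18 kg | 1,440 ml | 72 ml | 144 ml |

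All agree with Appendix E.

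**Step 2: one immune draw as a share of blood volume.**

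- 14 kg: 50/1,120 = 4.5%, which is 50/56 = 89% of the daily limit.
- 16 kg: 60/1,280 = 4.7%, which is 60/64 = 94% of it.
- 18 kg: 60/1,440 = 4.2%, which is 60/72 = 83% of it.
- 30 kg: 60/2,400 = 2.5%, half the limit.
- 50 kg: 60/4,000 = 1.5%.

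**Step 3: the 8-week limit.** Weeks 12 and 18 are 6 weeks apart, as are weeks 18 and 24, so two immune draws and one ctDNA sample fall in one 8-week window.

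- 14 kg: 50 + 50 + 6 to 7 = 106-107 ml of 112, leaving 5-6 ml for all safety laboratory tests in the window.
- 16 kg: 60 + 60 + 6 to 7 = 126-127 ml of 128, leaving 1-2 ml.

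So at the lowest weights the limits are nearly used up even when hematocrit is normal.

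**Step 4: how often.** Weeks 0, 12, 18, 24, 36, 48, 60, 72, 84 and 96 make up to 10 immune draws.

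**Step 5: set the assumption against the other sections.**

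- *No other therapies.* The sentence is in the present tense and temozolomide is prior treatment, so the permission weakens the inference to a normal hematocrit without contradicting the sentence. Nivolumab in Stratum C (Section 6) and Avastin, allowed for pseudo-progression (Sections 6.2.4 and 7.4), undercut it more directly.
- *Experience in DIPG.* For other midline gliomas this is extrapolation.
- *Eligibility.* There is no red-cell criterion, so eligibility cannot supply the condition.
- *CBC.* It is required, but no sentence connects it to the draw. For Stratum C the CBC at weeks 36, 48, 60, 72 and 84 comes from Section 7.1.2.6; the column heading of Table 6.2 does not list those weeks.

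**Step 6: how many children.** The documents do not say. At an assumed anemia rate of 5% to 20%, 1 to 4 of the 20 Stratum C children would be affected. This is only the assumed rate times 20, and the conclusion does not depend on it.

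**The case against.** The strongest reply is that the plan already contains the safeguards. A CBC is scheduled at the visits, so it would be wrong to infer that hematocrit goes unchecked; what is missing is an instruction on what the result means for the draw. That part of the reply stands.

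A reader might also infer that eligibility contradicts Appendix E. It does not. Temozolomide is allowed only during radiation, study treatment starts 2-8 weeks after radiation ends, and concurrent anti-cancer agents are excluded (Section 3.2.2). The grounds are incomplete, not refuted.

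Nor do the documents support the reading that anemic children are being drawn at full volume. They report no anemic participant and no anemia rate, and Appendix E describes the immune sample as an upper amount, although the only stated reason to vary it is weight.

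A same-day breach of the 5% limit from adding ctDNA or safety samples is not supported either. At 14 kg an immune draw plus ctDNA would be 56-57 ml against 56 ml, but Appendix E puts these on different days. That separation protects the daily limit; it does not change the 8-week total.

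Two further points stand. Most of the 3-21 age range has ample margin. And the documents do not show that a draw below 5% harms a mildly anemic child; that depends on the guideline Appendix E cites, which is not reproduced.

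**Conclusion.** The concern holds as a gap between a stated safety condition and the procedures meant to honor it. If the plan is followed as written, a child with a low hematocrit could be enrolled and have the full weight-based 50 or 60 cc taken, which Appendix E's own limits do not cover. The margin is thin only in the smallest children: 89% of the daily limit at 14 kg and 94% at 16 kg, with 1-6 ml left under the 8-week limit at those weights.

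This rests on the plan's figure of 80 ml/kg and its fixed volumes, and on the absence of any rule linking CBC to draw. It assumes nothing about how many children are anemic. Strata A and B have treated their full 19 and 10 patients (Section 5.1.5), so the practical target is Stratum C. A clarifying amendment is worthwhile and proportionate.

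**What to change.** Reconcile Appendix E with Sections 3.2.1 and 6:

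- Delete the expectation that all children have a normal hematocrit because they receive no other therapy.
- State that the fixed 50/60 cc volume applies only when the CBC already obtained for that visit, or within the previous 7 days, meets Appendix E's normal-hematocrit condition.
- Where it does not, have the investigators apply the limits in the guideline that Appendix E cites, and record any reduced or omitted research sample with that reason.

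This enforces the plan's own condition and sets no new clinical threshold.

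The cost is a wording change and no extra blood test, plus a few smaller or missing immune samples. Section 9.2 already gives ELISPOT priority over tetramer when cells are short. Because such samples may be missing for reasons related to health, that should be noted when CTL response is correlated with OS under Section 10.3.3; the recorded reason makes this possible.

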7.1.2.5 Study Procedures Day 1 of Week 24 (- 3 days)

Laboratory assessments do not need to be repeated if completed within 7 days prior.

- Physical examination including neurological examination
- Vital signs
- Pulse oximetry (Stratum C only)
- Performance status
- Evaluation of adverse events
- Concomitant medications
- CBC with differential and platelet count
- Blood chemistry assessment, including:
 - Alkaline phosphatase, ALT/AST, total bilirubin, calcium, phosphorus, BUN, creatinine, total protein, albumin, glucose, potassium, sodium, chloride, and bicarbonate
 - Lipase, amylase, and CRP (Stratum C only)
 - CPK and cardiac troponins (Stratum C only)
- TSH (if TSH is abnormal also measure free T4) (Stratum C only)
- UA (Stratum C only)
- Serum or urine pregnancy test for females of childbearing age
- Echo/ECG, as clinically indicated (Stratum C only)

Nivolumab (+/- 3 days; Stratum C only)

7.1.2.6 Study Procedures Day 1 of Week 27, 30, 33, 36, 39 etc. through Week 96 (- 3 days)

Laboratory assessments do not need to be repeated if completed within 7 days prior.

Stratum C only

- Physical examination including neurological examination
- Vital signs

- Pulse oximetry
- Performance status
- Evaluation of adverse events
- Concomitant medications
- CBC with differential and platelet count
- Blood chemistry assessment, including:
 - Alkaline phosphatase, ALT/AST, total bilirubin, calcium, phosphorus, BUN, creatinine, total protein, albumin, glucose
 - Lipase, amylase, and CRP
 - CPK and cardiac troponins
- TSH (if TSH is abnormal also measure free T4)
- UA
- Serum or urine pregnancy test for females of childbearing age
- Echo/ECG, as clinically indicated (Stratum C only)

Nivolumab (+/- 3 days; Stratum C only)

Vaccination (every 6 weeks, weeks 27, 33, 39, 45, 51, 57, 63, etc. through Week 96:

- Vaccination with K27M/TT
- IM injection of poly-ICLC

Post Vaccination:

- All patients will be closely observed for adverse events for at least 20 minutes following each vaccination. Any time thereafter, patients should report any adverse events to the research coordinator or research clinician.
- 7.1.2.7 Study Procedures Day 1 of Weeks 12, 24, 36, 48, 60, 72, 84, 96 (- 7 days) (All strata)

Laboratory assessments do not need to be repeated if completed within 7 days prior.

- Brain MRI (-14 days)
- Spine MRI if clinically indicated (-14 days)
- Circulating tumor DNA
- Immuno-monitoring assessments (also to be collected at Week 18)

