- 15. Day 1, each visit starting at Week 3 (excluding Week 24): as clinically indicated. **End of Treatment**: as clinically indicated.
- 16. Spinal MRI only required if clinically indicated. Post radiation therapy MRI must occur within 14 days of enrollment and within 14 days of treatment start date (Day 1 Week 0). MRI to be obtained at baseline and then every 12 weeks thereafter (-14 days) at Weeks 12, 24, 36, 48, etc.
- 17. To be obtained at weeks 0 (prior to vaccine), 12, 18, and 24 and then every 12 weeks thereafter each time a MRI is performed (-7 days) (i.e. Week 36, 48, 60, etc.). See Section 9 for further details.
- 18. To be obtained at baseline (Week 0 Day 1) and then every 12 weeks (-7 days).
- 19. If a patient has evidence of progressive disease and is undergoing tumor tissue resection as part of standard of care, a sample should be sent to UCSF for further analysis to assess antigen loss and immune cell infiltration. Please see Section 9.2.2 for further details. Please refer to PNOC SharePoint member website for shipping information.
- 20. Nivolumab to be given every 3 weeks. Nivolumab will be given IV before or after vaccine and poly-ICLC injection (+/- 3 days of vaccination and poly-ICLC injection).

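### Appendix E's fixed immune draws are checked against the 24-hour blood limit but not the 8-week limit, which can be exceeded around week 18 in the lightest children

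*Combined protocol and SAP*

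**What the plan says.** Appendix E takes blood volume as about 80 mL/kg and allows, for laboratory evaluations, 5% of it in 24 hours and "up to 10% of the whole blood volume over an 8 week period", provided the hematocrit is normal. It works out both limits at 14, 16 and 18 kg. It then fixes the immune-monitoring volume: "we will take 50 cc in green top tubes in children < 16 kg and 60cc in children >/= 16 kg". For ctDNA, "we will collect 6-7 ml at baseline and with each MRI assessment".

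Two safeguards follow. The first is "We will assure that recommended dose of 5% of total volume in a 24 hour period will not be exceeded". The second is "ctDNA and other laboratory evaluations will be scheduled on different days as required by the guidelines". No matching assurance is given for the 8-week limit.

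The Stratum C schedule is in Table 6.2. Footnote 17 sets the immune draws: "To be obtained at weeks 0 (prior to vaccine), 12, 18, and 24", then every 12 weeks. Section 7.1.2.7 agrees: after the 12-weekly list it adds "Immuno-monitoring assessments (also to be collected at Week 18". Footnote 18 sets the ctDNA samples: "To be obtained at baseline (Week 0 Day 1) and then every 12 weeks (-7 days".

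Sections 7.1.2.4 and 7.1.2.5 add safety bloods every three weeks. In Stratum C these are a blood count, chemistry, lipase, amylase, CRP, CPK, troponins and TSH. No volume is stated for them.

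**The concern.** The 8-week limit applies to all laboratory blood, not only research blood. The extra immune draw at week 18 puts two large draws six weeks apart, twice in succession. A volume chosen to fit a single day need not fit the sum over 8 weeks, and nothing visible in the plan controls that sum.

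At stake is a paediatric safety limit that the protocol sets for itself. A site could follow the stated volumes to the letter and still pass it in a small child. Strata A and B have completed accrual, so the point concerns Stratum C, which plans 20 patients from age 3.

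**Working it through.** **Inputs.** From Appendix E: blood volume 80 mL/kg; immune draw 50 mL below 16 kg and 60 mL from 16 kg; ctDNA 6-7 mL. From Table 6.2: immune draws at weeks 12, 18 and 24; ctDNA at weeks 12 and 24. From Sections 7.1.2.4 and 7.1.2.5: safety bloods every three weeks. The volume per safety visit is not given, so it is assumed below.

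**1. The plan's own limits.** 10% of 80 mL/kg is 8 mL/kg. This gives 8 × 14 = 112 mL, 8 × 16 = 128 mL and 8 × 18 = 144 mL. All three match Appendix E.

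**2. Which draws share a window.** Nominal spacing is 42 days. With the 7-day early allowance it is 35 to 49 days, always under 56. Weeks 12 and 24 are at least 168 − 7 − 84 = 77 days apart, so three immune draws never share a window. Each of the pairs 12/18 and 18/24 contains two immune draws, one ctDNA sample and, on nominal days, three safety visits.

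**3. Research blood in such a window.**
- Below 16 kg: 2 × 50 + 6 to 7 = 106-107 mL.
- From 16 kg: 2 × 60 + 6 to 7 = 126-127 mL.

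| Weight | Limit (mL) | Research blood (mL) | Share of blood volume | Left (mL) | Left per visit, three visits (mL) |
|---|---|---|---|---|---|
| 14 kg | 112 | 106-107 | 9.5-9.6% | 5-6 | 1.7-2.0 |
| 15 kg | 120 | 106-107 | 8.8-8.9% | 13-14 | 4.3-4.7 |
| 15.9 kg | 127.2 | 106-107 | 8.3-8.4% | 20.2-21.2 | 6.7-7.1 |
| 16 kg | 128 | 126-127 | 9.8-9.9% | 1-2 | 0.3-0.7 |
| 17 kg | 136 | 126-127 | 9.3% | 9-10 | 3.0-3.3 |
| 18 kg | 144 | 126-127 | 8.8% | 17-18 | 5.7-6.0 |

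Headroom does not rise steadily with weight. It falls sharply at 16 kg, where the draw steps up by 10 mL.

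**4. Weight at which research blood alone reaches 10%.** 106/8 = 13.25 kg and 107/8 = 13.4 kg, so about 13.3 kg.

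**5. Adding safety bloods.** With 7 mL ctDNA and three visits of v mL each (v is an assumption), the limit is exceeded below (107 + 3v)/8 kg, and again from 16 kg up to (127 + 3v)/8 kg.
- v = 2: 113/8 = 14.1 kg, and 133/8 = 16.6 kg.
- v = 5: 122/8 = 15.25 kg, and 142/8 = 17.75 kg.

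Children between the two bands, including those just under 16 kg, stay inside the limit at these volumes.

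**6. Whether the existing safeguards bound the sum.** Separate-day scheduling matters for the daily limit: at 14 kg, 50 + 7 = 57 mL on one day would pass 56 mL. It leaves the 8-week total unchanged. The 5% assurance caps one draw at 4 mL/kg. Two draws at that cap come to 8 mL/kg, the whole 8-week allowance, with nothing left for ctDNA or safety bloods.

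**The case against.** A reader might infer from the 14 and 16 kg figures that the plan already breaks its limit at those weights. It does not. At all three weights that Appendix E works out, the stated research volumes comply. A breach at 14 kg or above depends on safety-blood volumes that the documents do not give. A reader might also infer that every child under about 18 kg is affected. That is too broad: the affected weights form two bands, and a child just under 16 kg has more room than one at 18 kg. Nor is there an arithmetic error, since 112, 128 and 144 mL are correct. What is missing is a rule for the cumulative volume. All of this stands.

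The defence also notes that the appendix presents the draw as a maximum, says that volume depends on weight, and ties scheduling to the guidelines. A treatment delay under Section 6.2.2 may separate the draws. Collection instructions on the consortium's member website cannot be seen and might contain a cap. A blood count is taken at each visit. These points reduce the practical risk. They do not remove the gap, because the operative sentence fixes 50 or 60 mL by weight alone and only the 24-hour limit is assured.

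**Conclusion.** The point holds and is minor. Within the visible text, a stated volume rule is not reconciled with a stated 8-week safety limit. Research blood alone exceeds that limit below about 13.3 kg. Such a child is plausible: Appendix E gives 14 kg as the 50th percentile at age 3, and Section 3.2 sets no minimum weight. At 16 kg almost any safety blood passes the limit, since 0.3-0.7 mL per visit is all that remains.

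The wider bands rest on assumed safety volumes of 2 to 5 mL, three visits per window, 7 mL ctDNA, 80 mL/kg, draws at the full stated volume, and visits on schedule. Scope is confined to the two windows that share week 18 and to the lightest Stratum C children. Their number is unknown and may be zero. No primary endpoint is affected.

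**What to change.** In Appendix E, extend the existing 5% assurance to the 8-week limit. Each immune draw should be the smaller of 50/60 mL and 8 mL/kg minus all other blood (immune, ctDNA, safety) taken or due in the same 8-week window. Any reduction can come from the week 18 draw or be shared across the two draws. Week 18 belongs to both windows, so reducing it alone corrects both.

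For illustration, with 7 mL ctDNA, three safety visits of an assumed 2 to 5 mL, and the whole reduction at week 18, the week 18 draw would be:
- 14 kg: 112 − 50 − 7 − 6 = 49 mL, down to 112 − 50 − 7 − 15 = 40 mL.
- 16 kg: 128 − 60 − 7 − 6 = 55 mL, down to 128 − 60 − 7 − 15 = 46 mL.

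The text costs one sentence plus matching collection instructions. The scientific cost is a smaller cell sample in the lightest children. Section 9.2 runs ELISPOT first when cells are short, so the exploratory tetramer assay would lose data. Its response definition in Section 9.2.1 needs two consecutive positive time points, and week 18 sits between weeks 12 and 24, so a lost week 18 result could change a child's classification. Sharing the reduction across draws is the alternative if that matters.
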